Co-Investigator	[name] Senior Staff Specialist Medical Oncology Division of Cancer Services, Princess Alexandra Hospital, QLD Email: [contact]
Co-Investigator	[name] [name] A/Director Hepatobiliary Unit Division of Surgery, Princess Alexandra Hospital, QLD Email: [contact]
Co-Investigator	[name] Post-Doctoral Fellow University of Queensland Diamantina Institute (UQDI), Translational Research Institute, QLD Email: [contact]
Co-Investigator	[name] Staff Pathologist Pathology Queensland, Princess Alexandra Hospital, QLD Email: [contact]
Co-Investigator	[name] Radiologist and Nuclear Medicine Physician Radiology Department, Princess Alexandra Hospital, QLD Email: [contact]
Associate-Investigator	[name] Mater Research, Translational Research Institute, QLD
Associate-Investigator	[name] Nurse Researcher, Princess Alexandra Hospital, QLD
Associate-Investigator	[name] General Surgery, Toowoomba Hospital, QLD
Associate-Investigator	[name] Radiology Department, Princess Alexandra Hospital, QLD
Associate-Investigator	[name] Radiology Department, Princess Alexandra Hospital, QLD
Associate-Investigator	[name] Division of Cancer Services, Princess Alexandra Hospital, QLD
Associate-Investigator	A/[name] General surgery, Royal Brisbane and Women's Hospital, QLD
Associate-Investigator	[name] University of Queensland Diamantina Institute, Translational Research Institute, QLD

Study Synopsis

Title	The clinical utility of [⁶⁸ Ga]-labelled fibroblast activation protein inhibitor (FAPI) positron emission tomography and computed tomography (PET/CT) in patients with resectable or borderline resectable pancreatic ductal adenocarcinoma (PDAC) undergoing neoadjuvant chemotherapy.
Short Title	Clinical utility of [⁶⁸ Ga] FAPI PET/CT in patients with potentially resectable PDAC.
Study Design	Single-centre prospective, single-arm study.
Duration	18 months.
Site	Princess Alexandra Hospital, Woolloongabba, Brisbane.
Sample Size	Approximately 20 patients with newly diagnosed resectable or borderline resectable PDAC undergoing neoadjuvant chemotherapy.
Primary Objective	To assess whether [⁶⁸ Ga] FAPI PET/CT provides clinical benefit in patients with resectable or borderline resectable PDAC who have been referred for neo-adjuvant chemotherapy.

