This study is a single-centre, prospective study evaluating the utility and clinical benefit of [⁶⁸Ga] FAPI PET/CT in 20 patients deemed to have resectable or borderline resectable PDAC on initial clinical evaluation and are considered suitable for neoadjuvant chemotherapy with FOLFIRINOX. The FOLFIRINOX regimen is a currently accepted standard of care chemotherapy for resectable or borderline resectable PDAC. Patients will undergo FDG-PET/CT which is also accepted care in the work up of a patient with potentially resectable pancreatic cancer. Because [⁶⁸Ga] FAPI PET/CT remains an experimental imaging modality, any findings on [⁶⁸Ga] FAPI PET/CT that could alter patients' clinical decision making will be confirmed through biopsy or another established imaging modality and discussed at the HPB MDT meeting.

b. Study Site

This study will take place at Princess Alexandra Hospital (PAH), Woolloongabba, QLD, Australia. Metro South Health will be the primary sponsor for this study. The [⁶⁸Ga] FAPI isotope will be obtained from the Radiology department at the Royal Brisbane and Women's Hospital and couriered to PAH Radiology department in accordance with the "Code for the Safe Transport of Radioactive Material' guidelines.

Should there not be adequate recruitment of patients at PAH, feasibility to extend this study to include the Royal Brisbane and Women's Hospital will be considered.

c. Study Population

i. Sample Size

This study aims to recruit approximately 20 patients who have been referred to any hepato-pancreato-biliary (HPB) surgeon or medical oncologist within the PAH catchment. Any patient who fulfils the inclusion criteria, and is willing to participate in the study, will be included.

ii. Inclusion Criteria

- Age > 18 years
- Able to give informed consent
- Histological specimen from the primary pancreatic lesion confirming the diagnosis of PDAC.
- Patients need to have either a resectable or borderline resectable pancreatic lesion after imaging review at the HPB multidisciplinary (MDT) meeting
- No metastatic disease
- Eastern Cooperative Oncology Group performance status ≤ 1
- No contraindications to neoadjuvant chemotherapy.

iii. Exclusion Criteria

- Patients not medically fit for peri-operative chemotherapy with FOLFIRINOX or surgery
- Patients with known or suspected metastatic disease
- Pregnant or breastfeeding patients (if a female patient is pre-menopausal, she will require a negative urine pregnancy test prior to enrolment)

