All patients fulfilling inclusion criteria will be referred for PET/CT scanning as arranged by the coordinating investigator. Patients will first undergo [¹⁸F] FDG PET as part of pre-treatment workup, followed by [⁶⁸ Ga] FAPI PET/CT within approximately seven days.

Imaging procedures are as follows:

[¹⁸F] FDG PET: PET/CT imaging will be conducted after >6 hours of fasting and among patients with normal blood glucose levels. The dose of [¹⁸F] FDG is calculated according to the patient’s weight, 3.7MBq/kg. Static PET/CT imaging will be performed using the Siemens PET/CT scanner 60 minutes after intravenous injection and will include the skull base to upper thighs.

[⁶⁸ Ga] FAPI PET/CT: No specific preparation is required for [⁶⁸ Ga] FAPI PET/CT. The specific radioisotope used is the [⁶⁸ Ga]-FAPI-46 variant, and the dose is calculated according to the patient’s weight, 1.8–2.2 MBq/kg. Static PET/CT imaging will be performed using the Siemens PET/CT

scanner 60 minutes after intravenous injection and includes the base of the skull to the upper thighs.

b. Chemotherapy Protocol

Patients will receive four cycles of FOLFIRINOX within approximately seven days of completing both PET/CT scans at the PAH medical oncology unit. The FOLFIRINOX regimen is defined as follows:

Day 1 Oxaliplatin 70mg/m² IV over two hours
Irinotecan 150mg/ m² IV over 90 mins
Leucovorin 300mg/m² IV over 90mins
Flurouracil 300mg/m² IV bolus
Followed by
Days 1–2 Flurouracil 2.4g/m² IV continuous infusion over 46 hours
Repeat cycle every two weeks for 4 cycles

Approximately 28 days after the patient has completed their fourth cycle of chemotherapy, patients will repeat a [¹⁸F] FDG PET/diagnostic CT chest, abdomen and pelvis as part of their standard of care imaging, followed by a [⁶⁸ Ga] FAPI PET/CT within approximately 7 days.

c. Histological Analysis

After diagnostic requirements have been completed, pre-treatment biopsy specimens will undergo FAP immunohistochemistry (IHC). Tissue samples will be acquired from Queensland Pathology at PAH laboratory. FFPE blocks or slides will be transferred to Translational Research Institute (TRI) histology core facility for staining and analysis. Tissue samples will be stored in secure PC2 laboratory.

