- Dominant pattern of staining (i.e., stromal cells only, neoplastic cells only, or mixed).

7. Data Analysis and Statistical Methods

Descriptive statistics (frequencies and percentages) will be reported for categorical variables and interquartile range (IQR) will be reported for continuous variables.

We will compare the SUVmax response using a paired t-test or Wilcoxon rank-sum test for the following:

- [⁶⁸Ga] FAPI PET/CT and [¹⁸F] FDG PET/CT pre-chemotherapy
- [⁶⁸Ga] FAPI PET/CT pre- and post-chemotherapy
- [¹⁸F] FDG PET/CT pre- and post-chemotherapy

We will plot receiver operating characteristic (ROC) curves and calculate areas under the curve (AUCs) for each parameter to determine cut-points with optimal sensitivity and specificity. A two-sided P-value of <0.05 will be considered significant throughout.

For the patients' tissue analysis, we will perform linear regression, adjusting for potential confounders to determine if proportion and intensity of staining is related to SUVmax of primary pancreatic lesions. We will do this separately for both stromal and neoplastic expression. For each pattern of FAP expression (i.e., stromal cells only, neoplastic cells only, or mixed) we will determine median e SUVmax-p and IQR. We will compare groups using parametric or non-parametric tests depending on distribution of absolute SUVmax-p.

8. Data Management

a. Data Collection

Information required for this study will be collected directly from the participants and their medical records. Only the study investigators assigned to this research will have access to the patients' personal and medical information, pathology and initial imaging results and imaging data collected as part of the study.

b. Patient Confidentiality

Personal information and data collected will be treated in line with the Office of the Australian Information Commissioner's health privacy guidelines. In this study, data will be in re-identifiable form because data analysis and interpretation depend on patients' medical characteristics.

Participants in the study will have an identification code number allocated at enrolment. Patient data collected will be recorded under the participant's identification code. A code list linking the participant's identification number to their name will be kept by the Coordinating Principal Investigator in a password protected file in the Queensland Health secure server.

c. Data Security

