Participant imaging results reported by the nuclear medicine clinicians will be stored in computer files under password protection on secure servers. Only investigators in the research team have access to these files.

Clinical data will be recorded onto an electronic data capture system in a password-secured, firewall-protected network within Metro South Health. Only investigators in the research team have access to this, and all access will be audited by the Coordinating Principal Investigator.

Medical information or records in paper copies will be securely stored in locked facilities. All study-related documents and data collection forms will be archived in a secure environment for a minimum of 15 years. After this time, study data will be destroyed according to institutional policies.

9. Participant Safety/Risk Management

Additional procedures that a participant would receive in this study are [⁶⁸Ga] FAPI PET/CT scans pre- and post-chemotherapy.

a. Generic Risks

The risks and complications of the PET/CT procedure can include the following:

- Minor pain, discomfort and bruising as a result of the insertion of an intravenous cannula
- Physical discomfort related to positioning for the PET-CT scan
- A small amount of radiation to produce the PET images (details below)
- Infection from intravenous cannula site, which may require treatment with antibiotics
- An allergic reaction to injected tracer requiring further treatment.
- Death resulting from this procedure has not been reported

b. Risks Associated with Radiation Exposure

The dose of radiation a patient receives from a [¹⁸F] FAPI PET/CT at the PAH is approx. 10 millisieverts (mSv) and from [⁶⁸Ga] FAPI PET/CT is approx. 6.5mSv. The participants in this study will receive two [¹⁸F] FDG PET/CT scans, which is part of their standard of care therapy, and two [⁶⁸Ga] FAPI PET/CT scans. This equates to 23 mSv in total.

The annual occupational radiation exposure limit is 50 mSv per year, and even at this level, the increased cancer risk is so low that it cannot be measured against the normal incidence of cancer. It is, therefore, anticipated that participants will be at no increased risk of harmful effects from the PET/CT scans they receive.

c. Risks Associated with Injection of FAPI Ligand

Variations of the FAPI ligand, including [⁶⁸Ga]-FAPI-46, have been used in several human clinical trials to date. No adverse effects from an intravenous injection of radio-labelled FAPI have been identified.

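### The non-parametric option for the paired SUVmax comparisons is the Wilcoxon rank-sum test, which is for independent samples; it should be the signed-rank test

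*Protocol*

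**What the plan says.** Protocol Section 7 (Data Analysis and Statistical Methods) reads "We will compare the SUVmax response using a paired t-test or Wilcoxon rank-sum test for the following". Three comparisons follow: FAPI against FDG before chemotherapy, FAPI before against after chemotherapy, and FDG before against after chemotherapy. The same section adds "A two-sided P-value of <0.05 will be considered significant throughout".

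The rest of the protocol shows that all three are within-patient comparisons:

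- The Study Synopsis describes a "Single-centre prospective, single-arm study", so there is no second group of patients.
- Section 6a: "Patients will first undergo [¹⁸F] FDG PET as part of pre-treatment workup, followed by" a FAPI scan about a week later, so each patient has both tracers at baseline.
- Section 6b: "Approximately 28 days after the patient has completed their fourth cycle of chemotherapy, patients will repeat a" FDG scan, and then a FAPI scan, so the same patients are measured again with both tracers.
- Section 9b counts two FDG scans per participant, "which is part of their standard of care therapy, and two" FAPI scans.

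Section 7 has one other sentence on non-parametric testing: "We will compare groups using parametric or non-parametric tests depending on distribution of absolute SUVmax-p". It concerns groups of patients defined by FAP staining pattern, names no test, and does not govern the three SUVmax comparisons. The signed-rank test is not mentioned anywhere in the protocol.

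**The concern.** Section 7 offers two tests for the same data that make opposite assumptions. The paired t-test works on each patient's difference. The rank-sum (Mann-Whitney) test pools all the values, ranks them, and treats the two sets as coming from different people. The non-parametric counterpart of the paired t-test is the Wilcoxon signed-rank test.

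The protocol gives no rule for choosing between the two for these comparisons. The usual trigger is skewed data, which is a real possibility for SUVmax in about 20 patients. The analyst would then move from a paired to an unpaired analysis as well as from a parametric to a non-parametric one.

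These are the only tests named for Aim 1, and they also cover the before-after change on which Aim 3 rests. In a study this small, letting each patient act as his or her own control is the main source of precision. The rank-sum option gives that up.

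**Working it through.** **Inputs from the protocol.** About 20 patients (Section 5c.i: "This study aims to recruit approximately 20 patients"); two-sided 0.05 for each test (Section 7); both tracers at both time points in each patient (Sections 6a, 6b and 9b). The protocol states no power, effect size, SD or within-patient correlation, so it has no figure of its own to reproduce.

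**Assumptions.** SUVmax is log-normal with log-SD 0.5. The within-patient correlation ρ on the log scale is varied from -0.3 to 0.9. The true shift is 0 or 0.5 SD on the log scale; 0.5 SD is a ratio of exp(0.5 × 0.5) = 1.28. There are 20 complete pairs, with 14 as an assumed attrition case, and 20,000 simulated trials per setting.

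**Why the level is wrong.** The variance of a difference between two paired measurements is proportional to 2(1 − ρ). A test that assumes independence uses 2. A nominal critical value of 1.96 therefore acts as 1.96/√(1 − ρ), and the true two-sided level is roughly

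2 × [1 − Φ(1.96/√(1 − ρ))].

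- ρ = -0.3: 1.96/√1.3 = 1.72, level 0.086
- ρ = 0.3: 1.96/√0.7 = 2.34, level 0.019
- ρ = 0.5: 1.96/√0.5 = 2.77, level 0.0056
- ρ = 0.7: 1.96/√0.3 = 3.58, level 0.0003

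**Simulation, n = 20, nominal 0.05.** The approximation is rough at high ρ, but the pattern agrees.

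| ρ | Type I error, rank-sum | Type I error, signed-rank | Power at 0.5 SD, rank-sum | Power at 0.5 SD, signed-rank |
|---|---|---|---|---|
| -0.3 | 0.084 | 0.051 | 0.34 | 0.24 |
| 0 | 0.049 | 0.049 | 0.32 | 0.30 |
| 0.3 | 0.021 | 0.048 | 0.30 | 0.40 |
| 0.5 | 0.009 | 0.048 | 0.27 | 0.51 |
| 0.7 | 0.002 | 0.048 | 0.24 | 0.73 |
| 0.9 | <0.001 | 0.051 | 0.20 | 0.99 |

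The higher rank-sum power at ρ = -0.3 is bought with an inflated type I error. With 14 pairs and ρ = 0.5, the rank-sum type I error is 0.008 and power at 0.5 SD is 0.16, against 0.35 for signed-rank.

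A separate run on normally distributed data (n = 20, shift 0.6 SD, 4,000 trials per setting) gave rank-sum power of 43%, 43% and 42% at ρ = 0.3, 0.5 and 0.7, against 56%, 71% and 90% for signed-rank. The result does not depend on the log-normal form.

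**Constructed example.** Take 20 patients with baselines 5, 6, …, 24, whose values all rise, by 1.50 to 1.69 units. The rank-sum test gives p = 0.44, because the rise is small next to the spread between patients. The signed-rank test sees 20 positive differences out of 20 and gives p = 2 × (1/2)^20 = 0.0000019. A rise in every patient would be reported as no evidence of change.

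**The case against.** The case on the other side has five parts.

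1. **Only one of the two options is affected.** If the paired t-test is used, the pairing is kept. This is correct and limits the point to the non-parametric option. That option remains live, because nothing in Section 7 says when it will be used.
2. **It is probably a naming slip.** The test stands beside a paired t-test for plainly paired data, and many analysts would read it as signed-rank. That is likely, and it lowers the chance of harm. But Section 10 commits the study to following the protocol as written, and a literal reader would run an independent-samples test.
3. **The direction and size rest on assumed correlations.** This stands. Positive correlation is plausible for the same tracer in the same patient, and there the test is too conservative. Between FAPI and FDG the sign is not established. At zero correlation the test does no harm, and at -0.3 it rejects too often. A test whose level depends on an unknown correlation is still the wrong test.
4. **The power loss shrinks for large effects.** At a shift of 1.0 SD, rank-sum against signed-rank is 89% against 94%, 92% against 98% and 96% against 100% for ρ = 0.3, 0.5 and 0.7. At 1.3 SD both are at least 99%. This is correct, but the protocol does not say what effect it expects.
5. **The study is small and exploratory, makes no power claim, and does not base management on FAPI results.** This limits the consequences for patients. It does not make the named test valid, and the correction is free.

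**Conclusion.** The concern holds. The non-parametric test named in Section 7 does not fit the three comparisons to which it is assigned, and no other part of the protocol corrects it. This is a test wrongly specified in the protocol, not a detail left to a statistical analysis plan.

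If that option is used literally with positive within-patient correlation, the p-values are too large. Over assumed correlations of 0.3 to 0.7 with 20 pairs, the 5% test runs at between about 2% and 0.2%, and power for a moderate shift (0.5 SD) falls by about 10 to 50 percentage points (0.40 − 0.30 and 0.73 − 0.24). With negative correlation the p-values are too small. Only near zero correlation are they about right. The signed-rank test holds its level at 0.048 to 0.051 for every correlation tried at n = 20.

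The point should be corrected before analysis: it affects the only test named for Aim 1, and it could turn a real difference into a non-significant report.

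**What to change.** In Section 7, replace the rank-sum test with the Wilcoxon signed-rank test for all three SUVmax comparisons. That alone removes the error. The rank-sum test remains suitable where two independent groups of patients are compared, as with two FAP staining patterns.

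Preferably, though this is not needed to cure the error, fix one analysis in advance so that the choice of test does not depend on the data: for example a paired t-test on log SUVmax, reported as a geometric mean ratio with 95% confidence interval, with signed-rank as a sensitivity analysis.

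The cost is a one-line wording change, with no effect on patients, scans or data collection.

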A study performed by Choi et al. evaluated the use of [¹⁸F] FDG PET/CT in assessing response to neoadjuvant therapy in PDAC. This study showed that a decrease of more than 50% of standardised uptake value (SUV) on PET-CT was strongly predictive of R0 resection (19).

Ultimately, there is very little literature about the use of PET-CT scan for this indication. This raises the interest in evaluating [⁶⁸Ga] FAPI PET/CT as a marker of tumour response to neoadjuvant therapy in PDAC.

3. Aims/Objectives

The primary objective of this study is to assess whether [⁶⁸Ga] FAPI PET/CT provides clinical benefit in patients with resectable or borderline resectable PDAC who have been referred for neoadjuvant chemotherapy.

The specific aims of this study are as follows:

1. To compare the SUVmax of [⁶⁸Ga] FAPI PET/CT to [¹⁸F] FDG PET/CT in patients diagnosed with resectable or borderline resectable PDAC pre- and post-neoadjuvant chemotherapy.
2. To assess the percentage of fibroblast activation protein (FAP) expression in the pre-treatment biopsy specimen and the resected specimen and correlate this with [⁶⁸Ga] FAPI PET/CT SUVmax results pre- and post-neoadjuvant chemotherapy.
3. To assess the change in SUVmax on [⁶⁸Ga] FAPI PET/CT post neoadjuvant chemotherapy and correlate it with tumour response to chemotherapy determined on contrast enhanced CT scan and the resection specimen.

4. Hypotheses

For patients with potentially resectable PDAC this study sets out to prove that:

1. [⁶⁸Ga] FAPI PET/CT will be superior to [¹⁸F] FDG PET/CT in assessing tumour burden and its response to neoadjuvant chemotherapy.
2. Higher FAP expression in the tumour stroma will result in higher FAPI tracer uptake and is associated with a poorer response to neoadjuvant chemotherapy.
3. The change in SUVmax on [⁶⁸Ga] FAPI PET/CT following chemotherapy will correlate with response to treatment observed on contrast enhanced CT and pathological specimens. This correlation will be stronger than it is [¹⁸F] FDG PET/CT.

5. Methods

a. Study Design

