d. Risk Management

Safety monitoring and reporting will be performed in accordance with the NHMRC safety monitoring and reporting in clinical trials involving therapeutic goods guidelines. An annual safety report will be provided to the approving HREC for safety review and study continuation approval.

Potential risks are included in the participant information and consent forms. Participants are free to choose to participate based on their preference and assessment of potential risks. No study activity will take place until consent has been obtained.

The less common risks of infection from intravenous cannula site and reaction to injected tracer can be minimised by following standard operating procedures.

e. Adverse Event Reporting

Adverse events are unlikely but may occur due to reaction to the tracer or complications resulting from infection of the intravenous cannula site. Any adverse events will be reported to HREC as per routine reporting.

10. Ethical Considerations

This study is to be conducted in full conformance with all stipulations of the protocol, the conditions of the HREC approval, the NHMRC National Statement on Ethical Conduct in Human Research (2007), the principles of the “Declaration of Helsinki” and Good Clinical Practice. Study conduct will not commence until all necessary HREC, and Institutional Governance approvals and authorisations have been received.

11. Outcomes and Significance

Successful outcomes of this study could potentially:

- 1. Guide clinical decisions in the early management of patients with PDAC:*
We anticipate that [⁶⁸Ga] FAPI PET/CT will be superior to [¹⁸F] FDG PET/CT in determining initial tumour burden and tumour response to chemotherapy. This will better guide clinicians’ decisions concerning surgical or further treatment options resulting in decreased patient morbidity. This will also help determine the most cost-effective treatment plan.
- 2. Promote future trials looking at the use of [⁶⁸Ga] FAPI PET/CT as a screening tool:*
Should [⁶⁸Ga] FAPI PET/CT show high sensitivity in defining malignant pancreatic lesions, its use as a possible screening tool in high-risk patients could be investigated. This would lead to earlier intervention, improving clinical outcomes and decreasing mortality in patients with PDAC.
- 3. Promote theranostic trials:*

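### ROC cut-points are to be optimised in about 20 patients with no stated outcome; accuracy read off the same patients will on average be overstated, and separate AUCs do not compare the tracers

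*Protocol*

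**What the plan says.** - **ROC analysis (Protocol, Section 7).** The plan is to draw ROC curves and "calculate areas under the curve (AUCs) for each parameter to determine cut-points with optimal sensitivity and specificity". The section does not say which two groups the curves separate. It names no pre-set threshold, second cohort or resampling. It adds: "A two-sided P-value of <0.05 will be considered significant throughout".
- **Population.** The synopsis describes a "Single-centre prospective, single-arm study". Section 5c states: "This study aims to recruit approximately 20 patients". Inclusion requires "Histological specimen from the primary pancreatic lesion confirming the diagnosis of PDAC", and the exclusion list contains "Patients with known or suspected metastatic disease".
- **Measures (Section 6d).** SUVmax in tumour deposits, for each tracer, before and after four cycles: four measures in all.
- **Response.** Section 3 takes response from contrast-enhanced CT and from the resection specimen. Under Section 6c only patients still judged resectable go to surgery. No responder definition is given.
- **Hypothesis 3 (Section 4).** The change in FAPI SUVmax will correlate with response, and more strongly than for FDG.
- **Looking ahead (Section 11).** Screening work could be considered should "FAPI PET/CT show high sensitivity in defining malignant pancreatic lesions".
- **A published threshold (Section 2).** For FDG, an earlier study found that "a decrease of more than 50% of standardised uptake value (SUV) on PET-CT was strongly predictive of R0 resection".

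**The concern.** Three things in this short passage work against each other.

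1. **No outcome is named.** Sensitivity and specificity need a positive and a negative class. Everyone enrolled has histologically proven PDAC, so malignancy supplies no negatives. Response is the only patient-level classification left, but Section 7 does not say so.
2. **The cut-point is chosen for its accuracy in the sample.** A threshold picked because it performs best in a small sample owes part of that performance to chance. If its sensitivity and specificity are quoted from the same patients, they are too high on average. Doing this for each parameter and then favouring the best one adds a second layer of selection.
3. **The tracer comparison is missing.** One AUC per tracer does not test whether one is larger than the other. The paired tests listed in Section 7 compare SUVmax levels, not association with response.

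At stake are the accuracy figures and FAPI thresholds the study would publish. A tracer that carries no information about response could look moderately accurate, and a useful one could look better than it will prove in new patients.

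**Working it through.** **Figure to reproduce.** None. The protocol gives about 20 patients without a power or precision calculation.

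**Step 1: which ROC is possible.** With N = 20 there are 20 patients with PDAC and 0 without. Specificity for malignancy is 0/0, so an ROC for malignancy is undefined at patient level. Sensitivity alone can be estimated: 20 of 20 detected would have an exact 95% CI of 0.83 to 1.00. Response versus non-response remains.

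**Step 2: optimism at the selected cut-point.** The protocol gives no responder rate, attrition rate or effect size, so these are assumptions:

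- Splits (responders/non-responders): 10/10 and 6/14 for all 20 patients; 5/8 and 7/6 for a smaller subset of 13, such as those resected.
- Marker: normal with equal variances in both groups, separated by d = √2·Φ⁻¹(AUC).
- Cut-point: the one maximising Youden's J = sensitivity + specificity − 1 in the sample.
- Summary: mean of sensitivity and specificity, (1 + J)/2. *Apparent* is in the same patients; *new patients* is the true value of that cut-point in the population.

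Results of 8,000 simulated studies per row:

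| Split | True AUC | Apparent | New patients |
|---|---|---|---|
| 10/10 | 0.50 | 0.617 | 0.500 |
| 6/14 | 0.50 | 0.631 | 0.500 |
| 5/8 | 0.50 | 0.647 | 0.500 |
| 7/6 | 0.50 | 0.641 | 0.500 |
| 10/10 | 0.70 | 0.729 | 0.623 |
| 6/14 | 0.70 | 0.741 | 0.623 |
| 5/8 | 0.70 | 0.758 | 0.621 |
| 7/6 | 0.70 | 0.754 | 0.621 |

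For 10/10 and AUC 0.70, sensitivity/specificity appear as 0.78/0.68 against 0.67/0.57 in new patients. Apparent J is 0.459 and true J is 0.246, an excess of 0.459 − 0.246 = 0.21. With 100/100 patients the excess is 0.338 − 0.275 = 0.06, so the size of the problem comes from the small sample.

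**Step 3: what happens to the AUC.** Choosing a cut-point does not bias the AUC of one pre-specified parameter: its simulated mean was 0.70 for a true 0.70. It is imprecise. By Hanley-McNeil, with A = 0.70 and n₁ = n₀ = 10:

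- Q₁ = A/(2 − A) = 0.538; Q₂ = 2A²/(1 + A) = 0.576
- SE² = [A(1 − A) + 9(Q₁ − A²) + 9(Q₂ − A²)]/100 = (0.210 + 0.436 + 0.778)/100 = 0.0142, so SE = 0.119
- 95% CI = 0.70 ± 1.96 × 0.119 = 0.47 to 0.93

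The exact 95% CI for a sensitivity of 8/10 is 0.44 to 0.97.

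**Step 4: best of several parameters.** Section 7 does not list them. As an illustration, take six (before, after and change, for two tracers), none informative. The expected best AUC is:

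- independent, direction free: about 0.72 (10/10) to 0.74 (6/14)
- correlated, direction free: 0.70–0.71 (10/10), 0.71–0.73 (6/14)
- correlated, direction fixed in advance: 0.63–0.66 (10/10), 0.65–0.67 (6/14)

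The correlated rows assume pre-post correlation 0.5–0.7 and between-tracer correlation 0–0.7. The amount depends on the number of parameters, their correlation and, most of all, whether the direction is fixed.

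**The case against.** **The protocol does not claim specificity for malignancy.** A reader might infer from Section 11 that the ROC is meant to show that FAPI separates malignant from benign lesions. The text does not support this. Section 7 does not tie the ROC to malignancy. Section 11 speaks only of sensitivity, conditionally, as a reason for later research, and sensitivity can be estimated in an all-PDAC cohort. This stands: there is no malignancy claim to withdraw, only an outcome to name.

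**Much of the remedy is usually left to a SAP.** The SAP is not shown and could contain resampling, confidence intervals or an exploratory label; the protocol rules none of these out. It also does not say that the best parameter will be singled out. This stands in part. But the protocol does state the method, which is to optimise cut-points in about 20 patients, and that choice can be judged on its face. A correction in a SAP would reduce the optimism but not the imprecision.

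**The splits and the six parameters are assumptions.** This is so. The overstatement appears under every split tried. The six-parameter figures are illustrative only: change is computed from the before and after values, so the six cannot be independent, and Hypothesis 3 implies a direction for change.

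**The 50% decline is not a ready-made FAPI threshold.** A reader might infer that the figure in Section 2 can serve as one. It is an FDG result. The title of the cited study (reference 19) places it in neoadjuvant chemo-radiotherapy for locally advanced disease, and its outcome was R0 resection. This stands.

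**Participants are not exposed to a derived cut-point.** Sections 6d and 12 bar decisions from FAPI alone. This stands; the harm is to the published evidence.

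**Conclusion.** The concern holds in this form. Section 7 optimises cut-points without a stated outcome in about 20 patients, and response versus non-response is the only patient-level ROC the design supports. If accuracy is read off the same patients, the mean of sensitivity and specificity is overstated on average by about 0.12 to 0.15 for an uninformative marker (0.62–0.65 against 0.50). For true AUC 0.70 the overstatement is about 0.11 to 0.14 (0.73–0.76 against about 0.62). These sizes rest on the assumed splits, an equal-variance normal marker and the Youden rule. They are averages and need not hold in any single sample.

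It would go too far to say that the AUCs themselves are biased: one pre-specified parameter gives an unbiased but imprecise AUC. Selecting the best of several adds optimism of a size the documents do not fix. Separately, no analysis in Section 7 tests the comparative part of Hypothesis 3. The point should be corrected before analysis; it does not undermine the study as a whole.

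**What to change.** In Section 7 of the protocol:

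1. State that the ROC outcome is response to chemotherapy, and define responder for it.
2. Name percentage change in SUVmax as the main ROC parameter, with its direction; list any others as secondary.
3. Report the AUC with a 95% CI for each tracer, and the paired AUC difference (DeLong or bootstrap) as the test of the comparative part of Hypothesis 3.
4. Report any data-derived cut-point only with bootstrap optimism-corrected sensitivity and specificity, repeating the cut-point selection in each resample, and label it exploratory.
5. Optionally, show the more than 50% SUV decline from Section 2 as a pre-set reference value for FDG, with exact CIs. Note its chemo-radiotherapy, locally advanced setting and that it is not an established FAPI threshold.

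No new patients, scans or data are needed. The cost is some wording, a small amount of extra analysis, and accuracy figures that look less favourable and carry wide intervals.
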